### **Study B (see flow sheet below)**

Following the measurement of endogenous glucose production [EGP] in Study A, and after the double tracer OGTT visit, subjects who receive Byetta will be started on Byetta, 5 ug sc bid, and they will return for a follow up visit in 7 days (visit 4) at which time the Byetta will be increased to 10 ug sc bid, if tolerated. Subjects will return at days 14, 21, and 28 (visits 5, 6, and 7). If the Byetta dose cannot be increased to 10 ug bid because of side effects on the day 7 visit, the dose will be advanced on the subsequent visit (i.e., day 14 or 21 or 28), side effects permitting. On the day 28 visit the Double Tracer OGTT will be repeated with Byetta dosing at time zero of study (Visit 7).

Subjects who received dapagliflozin will continue on dapagliflozin, 10 mg/day, and will return for follow up visits at days 7, 14, and 21. At the day 28 visit the the DT-OGTT will be repeated. On the day of DT-OGTT, dapagliflozin will be given in the morning prior to the study. Note that this group will not receive Byetta and, thus, will allow us to determine how long the effect of dapagliflozin to increase EGP persists.

Subjects who received dapagliflozin plus Byetta will continue on dapagliflozin and Byetta, and will return for follow up visits at days 7, 14, and 21. At the day 28 visit the DT-OGTT will be repeated. On the day of the DT-OGTT, dapagliflozin will be given in this group will allow us to determine whether the ability of Byetta to inhibit the paradoxical rise in EGP observed with dapagliflozin can be blocked on a chronic basis.

Subjects who received the placebo will not be continued forward. However, these subjects will be allowed to be randomized to the Byetta alone, dapagliflozin alone, or Byetta/dapagliflozin groups.

**Visits 4, 5 and 6: Brief Follow Up Visits** for interim medical history and compliance with the treatment regimen a BMP will be done to check on your kidney function.

**Visit 7: Double Tracer OGTT** will be performed as per **Visit 3**.

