**Anticipated Results and Data Interpretation.** Consistent with our published data (10), we anticipate that EGP will decrease progressively following placebo administration while, after an initial decline, EGP will increase progressively following dapagliflozin. We anticipate that plasma glucagon conc will increase and plasma insulin concentration will decrease following dapagliflozin administration. We anticipate that a single administration of exenatide will cause an increase in plasma insulin conc and a decrease in plasma glucagon conc compared to placebo. The increase in plasma insulin and decrease in plasma glucagon conc following exenatide administration will result in a greater decline in both EGP and fasting plasma glucose conc compared to placebo. Most importantly, we anticipate that the increase in plasma glucagon conc, the decrease in plasma insulin conc, and rise in EGP following dapagliflozin administration will be prevented, at least in part, if not totally, when exenatide is co-administered with dapagliflozin. Therefore, we anticipate an additive, even synergistic, decrease in plasma glucose conc and EGP following co-administration of dapagliflozin plus exenatide compared to either drug alone.

**Sample Size Calculation:** In our published results (10), the difference in the rate of basal EGP during the last hour of EGP measurement in dapagliflozin-treated and placebo-treated individuals was  $0.70 \pm 0.34$  (mean  $\pm$  SD). To detect a 50% decrease in the difference at alpha = 0.005 ( $=0.5/10$ ) (split alpha for up to 10 multiple comparisons and a Bonferroni correction) in exenatide plus dapagliflozin versus dapagliflozin alone, we computed that 17 subjects in each group provided 90% power. To ensure 17 completers assuming 15% lost to follow-up, we have set the sample size at 20 ( $=17/0.85$ ) in each group.

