### **Study C (see flow sheet below).**

Following completion of the OGTT (Visit 7), subjects will be started on Bydureon, 2 mg sc per week. Subjects will return of interim follow up visits at weeks 6, 8, 10, 13-14, (visits 8, 9,10, 11. During the weeks 16-18 (visit 12),subjects will have a repeat Double Tracer OGTT (visit 12) will be performed..

**Visits 8, 9, 10, and 11. Brief Follow Up Visits** for interim medical history and compliance with the Bydureon regimen.

**Visit 12: Double Tracer OGTT** will be performed as per **Visit 3**.

The treatment period could be extended based upon the circumstances (based upon the situation of COVID-19 pandemic) until the repeat studies are completed.

**Data Analysis:** In **Study B**, we anticipate that dapagliflozin and Byetta will produce similar reductions in HbA1c and that the combination of dapagliflozin plus Byetta will produce an additive/near-additive reduction in A1c. We anticipate that both dapagliflozin and Byetta monotherapy will produce significant weight loss and that the combination will produce an additive, even synergistic, effect on weight loss.

We anticipate that that the dapagliflozin-induced rise in EGP will persist after 1 month in T2DM patients receiving dapagliflozin monotherapy even though both beta cell function and peripheral insulin sensitivity improve. We expect that Byetta-treated T2DM patients will experience a reduction in both fasting and postprandial plasma glucose levels during the DT-OGTT, markedly enhanced beta cell function, improved peripheral tissue insulin sensitivity, and reduced fasting and postprandial plasma glucagon concentrations during the DT-OGTT. In T2DM patients receiving combined Byetta/dapagliflozin therapy, we hypothesize that exenatide will block the dapagliflozin-induced rise in glucagon secretion and overcome the dapagliflozin-induced decrease insulin secretion, resulting in a greater suppression of EGP. Because we anticipate that Byetta will offset the negative effects of dapagliflozin on EGP and on insulin and glucagon secretion, we expect that the decline in fasting and postprandial glucose concentrations during the DT-OGTT will be enhanced in T2DM subjects receiving combination Byetta/dapagliflozin therapy.

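### Study B allows the delayed step to 10 ug Byetta on day 28, the day of the Visit 7 DT-OGTT, and does not state the test dose

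*Combined protocol and SAP*

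**What the plan says.** All references are to the combined protocol and SAP.

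- **Planned step.** In Study B, subjects on Byetta begin at 5 ug twice daily, and "they will return for a follow up visit in 7 days (visit 4) at which time the Byetta will be increased to 10 ug" twice daily if it is tolerated.
- **Delayed step.** If side effects prevent the day-7 increase, "the dose will be advanced on the subsequent visit (i.e., day 14 or 21 or 28), side effects permitting". The same paragraph numbers days 14, 21 and 28 as Visits 5, 6 and 7.
- **Outcome test.** "On the day 28 visit the Double Tracer OGTT will be repeated with Byetta dosing at time zero of study", which is Visit 7. The DT-OGTT sampling schedule places the injection at time zero together with the glucose load.
- **What follows.** Study C states: "Following completion of the OGTT (Visit 7), subjects will be started on Bydureon, 2 mg sc per week".
- **Expected acute effect.** Under Anticipated Results in Study A, the plan expects that "a single administration of exenatide will cause an increase in plasma insulin conc and a decrease in plasma glucagon conc" compared with placebo.

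**The concern.** Day 28 is both a permitted dose-advance day and the day of the Study B outcome test. A subject who could not step up on days 7, 14 or 21 may, as the text stands, be stepped up on the morning of the test. The time-zero injection would then be that subject's first 10 ug dose.

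Study B is the repeated-dosing stage. For the combination group, its stated question is whether Byetta's block of the dapagliflozin-induced EGP rise lasts with chronic treatment. Its Data Analysis text predicts better beta cell function and lower postprandial glucose and glucagon during this test. In a subject stepped up just before time zero, the post-load results would reflect four weeks at 5 ug twice daily plus an acute increase to a dose never taken before. The plan itself expects a single exenatide dose to move insulin and glucagon. The subject concerned is also one who was held back because of side effects, so the first larger dose would fall during a five-hour tracer study.

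**Working it through.** The point rests on setting the plan's statements side by side; the only arithmetic is a dose count.

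**1. The calendar.** Day 7 is Visit 4, and days 14, 21 and 28 are Visits 5, 6 and 7. The delayed-step list therefore covers every remaining visit, including the test visit.

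**2. The test dose.** Three places could fix it, and none does:
- The Study B text gives time zero but no amount.
- The DT-OGTT schedule gives the injection at time zero but no amount.
- Visit 7 is to be done as for Visit 3, and the Visit 3 description mentions no Byetta dose.

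No section says whether a day-28 step comes before or after time zero.

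**3. The two possible orders.**

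*Step before the test.* Assume twice-daily dosing with none missed, the test on day 28 exactly, and a step that takes effect with that day's first dose. For advance day *a*, the doses taken before the time-zero injection are 2 × *a* at 5 ug and 2 × (28 − *a*) at 10 ug.

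| Advance day | Prior doses at 5 ug | Prior doses at 10 ug |
|---|---|---|
| 7 | 2 × 7 = 14 | 2 × 21 = 42 |
| 14 | 2 × 14 = 28 | 2 × 14 = 28 |
| 21 | 2 × 21 = 42 | 2 × 7 = 14 |
| 28 | 2 × 28 = 56 | 2 × 0 = 0 |

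Only the day-28 row has a 10 ug test dose with no earlier exposure to 10 ug.

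*Step after the test.* No Study B measurement follows it, and Study C replaces Byetta with weekly Bydureon once the test is complete. The step has no planned Byetta period in which to act.

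Under either order, listing day 28 gains nothing for Study B.

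**4. Which measures are reached.**
- *Reached:* the Visit 7 measures taken after the load, namely insulin secretion, the Matsuda index, beta cell function, glucagon suppression and post-load glucose and EGP.
- *Not reached:* basal EGP and fasting hormones, because the basal samples (−60 to 0 minutes) precede the injection. The Study B sample size is built on basal EGP, combination versus dapagliflozin alone.
- *Not reached:* HbA1c and weight, which one injection on the test day does not move meaningfully.
- *Not reached:* the Study A primary endpoint, which is measured earlier, and Visit 12, which follows months on Bydureon.

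**5. Size.** A size would need the number of subjects still at 5 ug on day 28, the acute difference between 5 and 10 ug on each index, and the spread of those indices. The documents give none of these. The group sizes at Visit 7 are not fixed either, because placebo subjects may re-enter: "these subjects will be allowed to be randomized to the Byetta alone, dapagliflozin alone, or Byetta/dapagliflozin groups". No estimate is offered.

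**The case against.** The strongest reply is that the list simply names the remaining visits. Nothing directs that a day-28 step be made before time zero, and a step made after the test leaves the Study B data untouched. Further, every Byetta subject is injected at time zero, so acute and chronic effects are mixed in all of them. The plan already accepts between 14 and 42 earlier 10 ug doses among subjects stepped by day 21. The proposed change replaces a first 10 ug test dose with a 5 ug test dose, which is another form of dose variation. No powered quantity is touched, and there may be no affected subjects.

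Most of this stands. The mixing of acute and chronic effects is general and is not created by the day-28 option. Preferring a test at the established dose is a judgement about what Study B is meant to measure.

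Two things remain. The order is not stated, so two investigators following the text could treat the same subject differently. And the day-28 option has no useful function under either order, so removing it costs no planned Byetta treatment.

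A reader might infer that the two Byetta groups are given different doses, because the combination paragraph has no titration rule of its own. The documents do not support that: the titration text is addressed to subjects who receive Byetta and can be read to cover both groups. It is only a reason to say so explicitly.

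**Conclusion.** The point holds as a minor defect in a stated rule. Followed as written, the plan can make a subject's first 10 ug dose the Visit 7 test dose, and it never says what that dose should be. The consequence is confined to post-load Visit 7 measures in subjects who failed to step up on days 7, 14 and 21 and were then advanced before time zero on day 28. That number may be zero, and the size of any shift cannot be given from the documents. The dose count of 56 and 0 assumes full adherence and a test on day 28 exactly.

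Two stronger readings are tempting and are not supported:
- *That the overlap undermines the Study B comparison on which the sample size is based.* That comparison concerns basal EGP, which is sampled before the injection.
- *That it biases group means by some quotable amount.* The documents contain no rate of late titration and no dose-response figure from which to derive one.

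**What to change.** In the Study B titration sentence, replace the list of days with: *at a subsequent visit before Visit 7 (day 14 or 21, or a later visit if Visit 7 is postponed), side effects permitting*.

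Then add, for both Byetta groups: *the time-zero Byetta injection at Visit 7 is the dose the subject is already taking; no dose increase is made on the day of the test*.

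Tying the rule to Visit 7, not to a calendar day, keeps a later step available if the test is delayed. Study C provides that "The treatment period could be extended based upon the circumstances (based upon the situation of COVID-19 pandemic) until the repeat studies are completed". Whether this extends to Visit 7 is not stated, and the wording works either way.

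Report, by Byetta group, the number of subjects at 5 ug and at 10 ug at Visit 7.

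The cost is one phrase replaced, one sentence added and one count reported, with no extra subjects, visits or assays. The downside is that a few subjects may be tested at 5 ug instead of 10 ug. The plan already accepts that possibility by making the increase conditional on tolerance.

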**Data Analysis and Statistical Methods:** The **primary end point** of the study is the change in EGP during **Study A**. The difference in the rate of EGP during the last hour of the study (i.e. from 240-300 minutes) between drug-treatment and placebo-treatment studies represents the effect of drug treatment on EGP. The difference in EGP will be compared among the 3 drug treatments (exenatide, dapagliflozin, and exenatide plus dapagliflozin) with ANOVA. Post hoc testing will be performed with a Bonferroni correction for multiple

comparisons. The following primary comparison will be performed: (i) the change in EGP above baseline following dapagliflozin alone versus dapagliflozin/exenatide. The following secondary comparisons will be made: (i) the change in EGP above baseline following exenatide alone versus dapagliflozin/exenatide and (ii) the change in EGP above baseline following dapagliflozin alone, exenatide alone, and dapagliflozin/exenatide versus the change in EGP following placebo. Between group comparisons will be made with repeated measures ANOVA with time and treatment group as factors.

**Other secondary end points** will be: (i) the decrement in the fasting plasma glucose conc at the end of the study compared to baseline, (ii) change in plasma glucagon conc at the end of the study compared to baseline; and (iii) change in plasma insulin conc at the end of the study compared to baseline. Secondary end points will be compared using the same statistical methods described for the primary end point.

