**Sample Size Calculation:** In our published results (10), the difference in the rate of basal EGP during the last hour of EGP measurement in dapagliflozin-treated and placebo-treated individuals was  $0.70 \pm 0.34$  (mean  $\pm$ SD). To detect a 50% decrease in the difference at alpha = 0.167 ( $=0.5/3$ ) (split for 3 comparisons and a Bonferroni correction) in Byetta plus dapagliflozin versus dapagliflozin alone, we computed that 13 subjects in each group will provide 90% power.

**Data Analysis:** In **Study C**, we anticipate that dapagliflozin and Bydureon will produce similar reductions in HbA1c and that the combination of dapagliflozin plus Bydureon will produce an additive/near-additive reduction in A1c. We anticipate that both dapagliflozin and Bydureon monotherapy will produce significant weight loss and that the combination will produce an additive, even synergistic, effect on weight loss.

We anticipate that that the dapagliflozin-induced rise in EGP will persist after 4 months in T2DM patients receiving dapagliflozin monotherapy even though both beta cell function and peripheral insulin sensitivity improve. We expect that Bydureon-treated T2DM patients will experience a reduction in both fasting and postprandial plasma glucose levels during the OGTT, markedly enhanced beta cell function, improved peripheral tissue insulin sensitivity, and reduced fasting and postprandial plasma glucagon concentrations during the DT-OGTT. In T2DM patients receiving combined Bydureon-dapagliflozin therapy, we hypothesize that exenatide will block the dapagliflozin-induced rise in glucagon secretion and overcome the dapagliflozin-induced decrease insulin secretion, resulting in suppression of EGP. Because we anticipate that Bydureon will offset the negative effects of dapagliflozin on EGP and on insulin and glucagon secretion, we expect that the decline in fasting and postprandial glucose concentrations during the DT-OGTT will be enhanced in T2DM subjects receiving combination Bydureon/dapagliflozin therapy.

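### Study B says the dapagliflozin-only arm will show how long the EGP rise lasts, but with no placebo after Study A and EGP re-measured only at day 28 and weeks 16-18, the design cannot give a duration or a controlled drug effect

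*Combined protocol and SAP*

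**What the plan says.** Study B gives the dapagliflozin-only arm a specific purpose: it "will allow us to determine how long the effect of dapagliflozin to increase EGP persists". The same section sets the conditions under which that must be answered.

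- **Comparator.** "Subjects who received the placebo will not be continued forward"; instead, "these subjects will be allowed to be randomized to the Byetta alone, dapagliflozin alone, or Byetta/dapagliflozin groups".
- **Measurement times.** For the dapagliflozin arm, "At the day 28 visit the the DT-OGTT will be repeated". Visits 4 to 6 are "for interim medical history and compliance with the treatment regimen a BMP will be done"; no tracer is given. Study C adds one more double-tracer OGTT (DT-OGTT) at weeks 16-18.
- **Definition of the effect.** Under Data Analysis and Statistical Methods in Study A, the EGP difference at 240-300 minutes "between drug-treatment and placebo-treatment studies represents the effect of drug treatment on EGP".
- **Expected findings.** The Study B analysis text expects the rise to be present still at 1 month. The Study C text expects that "the dapagliflozin-induced rise in EGP will persist after 4 months in T2DM patients receiving dapagliflozin monotherapy".

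No comparator or analysis for persistence is named. The Study B sample size concerns the combination against dapagliflozin alone.

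**The concern.** A duration needs repeated measurements over time, and a drug effect, as this protocol defines it, needs a placebo group. Study B has neither. In the dapagliflozin-only arm, the available information on monotherapy is a before-after change, which mixes the drug with the passage of time and with repeat testing.

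At stake is a stated purpose of one of the three continuing arms. A change from Visit 3, or the lack of one, could be reported as persistence or loss of a dapagliflozin effect that the comparison does not isolate. Because the plan does not say whether Visit 3 is on or off drug, the same result could be read in either direction.

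**Working it through.** **1. The plan's own figure.** The Study B sample size uses a difference of 0.70 with SD 0.34, a 50% decrease (0.35), a printed alpha of 0.167 and 90% power. The two-sample normal formula is n = 2 × [SD × (z for alpha + z for power) / difference]². Two-sided, this is 2 × [0.34 × (1.382 + 1.282) / 0.35]² = 13.4, so 14 per group; at 13 per group the power is 89.3%. The stated 13 is therefore reproduced to within one subject. It is sized for the combination against dapagliflozin alone. Both of those arms take dapagliflozin, so the figure says nothing about persistence.

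**2. What the measurement times can show.** Suppose the effect could be identified at each test.

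| Day 28 | Weeks 16-18 | What is learned about duration |
|---|---|---|
| absent | – | ended at an unknown time before day 28 |
| present | absent | ended between 4 and 16-18 weeks |
| present | present | longer than 16-18 weeks |

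Study B alone supplies only the first split. The second and third rows also require the dapagliflozin-only arm to be on monotherapy at weeks 16-18. The Study C treatment text starts subjects on Bydureon without exempting that arm, while the Study C analysis text assumes dapagliflozin monotherapy at 4 months.

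**3. What the remaining arms can estimate.** Write P, D, B and BD for mean EGP on placebo, dapagliflozin, Byetta and the combination. The protocol's effect is D − P. At day 28 there is no P. The three available contrasts are:

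- BD − D: the effect of adding exenatide; dapagliflozin is in both arms.
- D − B: a mixture of the two drug effects.
- BD − B: the dapagliflozin effect in the presence of exenatide.

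The last equals D − P only if BD − B − D + P = 0, that is, if there is no interaction. The protocol expects exenatide to prevent the rise, partly or wholly. Take the planning value D − P = 0.70 as fully persisting. Then BD − B would be 0.70 with no interaction and 0 if exenatide removes the rise entirely. It cannot tell a lost monotherapy effect from a blocked one.

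**4. Whether the measure is the same.** Study A measures fasting EGP for 5 hours after dosing. The DT-OGTT table gives 75 g of glucose at time zero, so its 240-300 minute window is post-load. Only the pre-glucose samples are fasting.

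**5. What Visit 3 is.** The DT-OGTT table lists dapagliflozin at -30 minutes, and Study B says that these subjects continue on the drug. The plan does not say whether the table's dosing applies at Visit 3 or whether drug is taken between Visits 2 and 3. If the Visit 3 fasting samples are drug-free, no change at day 28 suggests that the effect is absent. If they are on drug, no change suggests that it persists.

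**6. Illustration of an uncontrolled test.** The chance that a one-sample t-test (two-sided 0.05) declares a change when the shift is not due to drug comes from the noncentral t with parameter shift × √n / SD. Shifts, SD and test are all assumed.

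| n | SD of change | shift 0.1 | shift 0.2 | shift 0.3 |
|---|---|---|---|---|
| 17 | 0.34 | 21% | 62% | 93% |
| 13 | 0.34 | 17% | 50% | 83% |
| 13 | 0.68 | 8% | 17% | 31% |

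The 17 is Study A's completer count and the 13 is Study B's group size. The 0.34 is the SD printed with the dapagliflozin-placebo difference, not a within-person SD over 28 days.

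**The case against.** The case on the other side is substantial, and several parts of it stand.

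- **The working hypotheses are already tied to time points**, 1 month and 4 months, so the duration wording is one loose sentence. This is true, and it limits the correction. It does not supply the missing comparator, which those two statements need as well.
- **No within-arm test is prescribed.** This stands. The plan names no persistence analysis at all, so the before-after change is what the design leaves, not what the plan specifies. Alpha is split for three comparisons, which may be the three pairwise contrasts among the continuing arms, and the Study B flow sheet is not visible. As step 3 shows, none of those contrasts is D − P.
- **Drift over 28 days is not shown.** A reader might infer it from the statement that "we anticipate that EGP will decrease progressively following placebo administration". That fall is within a single test day, and Visit 7 repeats the Visit 3 procedure, so it gives no size for drift between visits. It shows only that the authors do not treat untreated EGP as flat.
- **The table in step 6 is constructed.** This stands. A reader might take 62% as a false-finding rate for this trial; the documents support no such rate.
- **BD − B is a concurrent contrast.** A reader might therefore take it as the controlled answer on monotherapy. The protocol's own hypothesis rules that out.

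**Conclusion.** The stated purpose goes beyond the design. Duration cannot be determined. Persistence at day 28 under dapagliflozin alone can be examined only through an uncontrolled within-arm change, whose meaning depends on an undefined Visit 3. This rests on the text: one tracer test in Study B, one more in Study C, and a placebo group that goes from 20 to none. It needs no assumed SD or drift.

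The size of any resulting bias is unknown. A reader might infer that the trial's main result is compromised; it is not, because the primary endpoint belongs to Study A, which has its placebo arm. Nor do the documents show that a persistence finding would be false, only that this design could not establish it. The correction should be made because it changes what may be concluded from one arm and is mostly a matter of wording.

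**What to change.** 1. In Study B, replace the duration claim with: whether fasting (pre-glucose) EGP at day 28 differs from the Visit 3 value. Report the change with a 95% CI, labelled as an uncontrolled within-arm change that cannot separate drug from time or repeat-test effects.
2. State whether the Visit 3 fasting samples are drug-free, and reconcile the DT-OGTT table's -30 minute dosing with the Study B wording that subjects continue on dapagliflozin. Say beforehand how an unchanged EGP will be interpreted.
3. Limit the 1-month and 4-month persistence statements in the same way.
4. Reconcile the Study C treatment text, which starts subjects on Bydureon without exempting the dapagliflozin-only arm, with the Study C analysis text, which assumes dapagliflozin monotherapy at 4 months.
5. If the combination is compared with Byetta alone, report it with a 95% CI as the dapagliflozin effect in the presence of exenatide, and state that it is not a test of monotherapy persistence.

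None of this needs new visits, subjects or samples. The cost is a weaker monotherapy claim. Keeping the protocol's duration aim would require a concurrent control and more EGP time points, which is a far larger change.
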